1. INTRODUCTION

The noradrenergic system, and β -Ars in particular, are promising therapeutic targets for cognitive diseases such as Alzheimer's disease (AD) and Parkinson's disease (PD). In multiple transgenic mouse models of AD, xamoterol, a β -AR agonist, enhances cognitive function associated with the disease (Ardestani 2017, Coutellier 2014, Faizi 2011, Faizi 2012, Salehi 2009). Xamoterol additionally attenuates three major pathological hallmarks of AD: beta-amyloid burden, tau pathology, and neuroinflammation (Ardestani 2017). Collectively, these data suggest that targeting β -AR may have the unique potential to provide comprehensive therapeutic benefits for the treatment of AD.

Several epidemiologic studies additionally suggest that treatment with β -AR agonists may be more protective against development of PD (Aaseth 2018, Clark 2018, Gronich 2018, Magistrelli 2020, Mittal 2017, Searles 2018). Additional data also suggest that the effect of β -AR agonists may generalize to other cognitive disorders such as mild cognitive impairment (MCI) and AD (Chalermpalanupap 2013, Coutellier 2014).

The locus coeruleus (LC) is a small nucleus located in the pons and is the primary source of noradrenaline (norepinephrine) in the forebrain (Brunnström 2011). LC axons project to multiple cortical and subcortical regions that underlie memory, attention, and emotional processing, including the hippocampus, frontoparietal cortex, and amygdala (Berridge 2003). Through its binding to both α and β -adrenoceptors, noradrenaline plays a key role in a variety of essential central nervous system (CNS) functions such as learning and memory, arousal, attention, and cognition, and plays an important role in maintaining brain homeostasis by regulating neuroimmune responses.

Neuroanatomical studies have identified the LC as one of the earliest sites in the brain affected in cognitive diseases including AD and PD (Braak 2011, Braak 2017). Consistent with this, profound degeneration of noradrenergic neurons is an established early finding of AD, and deficits in noradrenergic neurotransmission have been described both in human patients and mouse AD models (Adolfsson 1979, Bondareff 1987, Grudzien 2007, Hoogendoorn 1999, Iversen 1983, Kalaria 1989, Tejani-Butt 1993). Importantly, the dysfunction of the noradrenergic system is tightly linked to both cognitive symptoms of AD and underlying disease progression at many levels such as neuroinflammation (Bondareff 1987, Heneka 2002, Jardanhazi-Kurutz 2010).

[figure not shown]
Progressive and extensive degeneration of the LC is evident early in patients with AD or PD (Kalaria 1989, Vermeiren 2017), giving rise to a hypothesis that the LC is a "ground zero" for the pathology underlying the development of cognitive impairment, and nonmotor symptoms and can further complicate the lives of PD patients (Nahimi 2018).

The role of β_2 -AR extends beyond neurotransmission (Figure 1). Expression of β_2 -Ars is observed across multiple cell types including neurons, nerve fibers, microglia, astrocytes, oligodendrocytes and blood vessels (Gao 2016). This diversity in cellular localization gives rise to a corresponding diversity of function. For example, β_2 -Ars have been shown to promote glycogenolysis and lactate release from astrocytes which contribute to memory consolidation and long-term potentiation of synaptic strength in hippocampal neurons (Sorg 1991, Gao 2016, Suzuki 2011). Hypometabolism is an early feature of neurodegeneration in Alzheimer's and Parkinson's diseases (Cunnane 2020, Sonninen 2020),

and it is thought that glial metabolic support of neurons is neuroprotective in the context of disease (Cai 2019, Cunnane 2020). A pro-metabolic role of β -AR stimulation has been variously demonstrated: adrenergic stimulation alters the cellular metabolism of astrocytes (Dienel 2016), increased cellular cyclic adenosine monophosphate (cAMP), the second messenger produced by β -AR signaling, is associated with enhanced glycolysis (Vardjan 2018), and stimulation of β -ARs increases cellular glucose uptake (Catus 2011) and glycogenolysis (Hertz 2010).

Finally, it is hypothesized that normal noradrenergic signaling from the LC may protect against inflammation, and that neuroinflammation in degenerative diseases may result from the progressive damage to the LC. This is supported by nonclinical observations that neurotoxin-mediated lesioning of the LC induces neuroinflammation (Pugh 2007), while stimulation of β_2 -AR expressed on microglia and astrocytes appears to be anti-inflammatory effect (reviewed by O'Donnell 2012).

Figure 1 **Heterocellular Role of Noradrenaline Projections from the Locus Coeruleus in Cognition**

Source: Giorgi 2019

Clinical and nonclinical studies conducted by CuraSen provide supportive evidence that CST-2032 mediates the diverse cellular functions described above. Firstly, in vitro studies confirm that CST-2032 stimulates β_2 ARs endogenously expressed on neuronal cells, astrocytes, microglia, pericytes, cerebral microvascular endothelial cells and human brain vascular smooth muscle cells to produce cAMP with similar potencies. Furthermore, nonclinical studies with CST-2032 demonstrate its effects on aspects of the neuronal, metabolic, and inflammatory signaling as described above. Specifically, CST-2032 improves performance a rat model of attention and impulsivity, in the five-choice-serial reaction test. Anti-inflammatory effects of CST-2032 were demonstrated in mice in the form of a reduction in lipopolysaccharide-mediated increases in pro-inflammatory mediators including TNF α and IL-6 in plasma and brain, and a potentiation of the anti-inflammatory IL-10. Finally, in an astrocytoma cell line that endogenously expresses β_2 -AR, CST-2032 shifted cellular metabolism away from mitochondrial oxidative phosphorylation and towards glycolysis, increasing the total rate of cellular ATP production.

In humans, increases in cerebral perfusion, measured as cerebral blood flow (CBF) by arterial spin labelling magnetic resonance imaging (ASL MRI) in brain regions relevant to cognition, attention and arousal, the thalamus, hippocampus and amygdala, were observed following administration of a β_2 -AR agonist, clenbuterol, in a clinical study sponsored by CuraSen Therapeutics, Inc (CST103/CST107/CST-109-CLIN-002). Similarly, improvements in performance in CANTAB domains were observed following administration of CST-2032 in healthy volunteers and subjects with MCI in the phase 1 study, CST2032-CLIN-007 ([Figure 2](#)). Increases in cerebral perfusion are expected under conditions of increased neuronal activity. This phenomenon of neurovascular coupling arises from integrated responses from multiple cell types, many of which are known to express β_2 receptors, including neurons, cerebral blood vessels, microglia, oligodendrocytes, and astrocytes ([Giorgi 2020](#)).

Taken together, LC neuronal loss and the resulting widespread consequence of noradrenergic deficiency in neuronal transmission, metabolism and inflammation are believed to underpin cognitive impairment in neurodegenerative diseases. We hypothesize that this noradrenergic deficiency may be restored through exogenous adrenergic stimulation using the β_2 -AR agonist, CST-2032.

The CLIN-015 study seeks to evaluate the safety and efficacy of CST-2032 when dosed with CST-107 in subjects with mild cognitive impairment or mild dementia where the disruptions in noradrenergic stimulation, metabolism and inflammation described above have been reported. In addition, secondary analyses will evaluate the effects of treatment on cognition, mood and attention, and the pharmacokinetic (PK) properties of CST-2032 when administered with CST-107. As exploratory objectives, this study may additionally evaluate whether baseline disease characteristics such as disease activity, neurodegenerative biomarkers in the plasma and Apolipoprotein E4 variant influence the effects of treatment.

Use of an agonist for stimulating β_2 -ARs within the CNS represents a novel approach in any neuropsychiatric indication, largely due to concerns about how such an agonist action in the brain could be selectively precipitated, while sparing likelihood of excess stimulation of the same target in the periphery. Excess stimulation of β_2 -ARs in the periphery has the potential to cause AEs of cardiovascular and metabolic origin. Accordingly, the concept of co-administering a β -AR antagonist ('beta blocker') that has both preference for the β_2 -AR subtype, and minimal CNS penetration, was developed. Examination of the large number of widely used β -AR antagonists revealed one established antagonist, nadolol (CST-107), as uniquely fitting this need, assuming that an optimal dose level could be identified that preferentially blocked only β_2 AR function in the peripheral tissues, with low access to desired CNS targets. CuraSen's data from the CLIN-007 study identified the doses of nadolol that effectively minimize the peripheral effects of CST-2032. These doses are less than 10% of the lowest dose for nadolol approved for treatment of angina or hypertension (40 mg) and are likely to preferentially inhibit β_2 -ARs. The CLIN-007 study additionally confirmed that only 2 to 3 % of the plasma concentration of nadolol is detected in the cerebrospinal fluid, supporting the use of this combination dosing therapeutic strategy, that will eventually require formulation of a fixed dose combination drug product.

1.1. Rationale for Dose Selection

1.1.1. Rationale for CST-2032 Dose Selection

β_2 -AR agonists have been used for decades as bronchodilators for treatment of bronchospasm in patients with obstructive airway disease. As such, peripherally mediated the pharmacologic effects and risks associated with this class of agent are well known, including increased heart rate, hyperglycemia, hypokalemia, muscle twitch and tremor, palpitations, and peripheral vasodilatation (see [Ventolin \[albuterol\] HFA label](#)).

It is understood that these peripherally mediated effects may not be ideal properties for a medication for use in long-term patient studies. Accordingly, the use of doses of CST-2032 that might produce significant changes in these peripheral measures can only be safely contemplated if simultaneously co-administered with a dose of an antagonist for these β_2 -AR mediated effects, but one that fails to significantly cross the blood brain barrier, thus leaving the cerebral β_2 -AR population sensitive to a CNS penetrant agonist such as CST-2032. The dose levels of CST-2032 proposed for this study therefore have been selected to be administered along with such peripherally restricted antagonist, thus attenuating any of the clinical effects listed above.

At the doses of 3 mg of CST-2032 and 3 mg of nadolol planned for the CLIN-015 study, there were no clinically significant increases in heart rate, prolongation of QTcF, or decreases in potassium levels observed in the CLIN-007 study. Furthermore, there were no instances of tremor, palpitations, dizziness, or tachycardia. Therefore, it is expected that the combination of 3 mg CST-2032 with 3 mg of nadolol will be safe and well tolerated.

In rats and dogs, the NOAELs observed with CST-2032 were determined to be 110 and 15 mg/kg/day, respectively, the highest doses tested in the GLP 28-day repeated-dose toxicity studies. Based on the CLIN-007 study, the plasma exposures observed at the dose of 3 mg CST-2032 are 588- and 193-fold below the AUC₀₋₂₄ at the no-observed adverse event levels in 28-day toxicity studies in rat and dog ([Investigator Brochure \[IB\]](#)).

The 3 mg dose of CST-2032 to be administered in CLIN-015 has previously been administered as single and once-daily doses for 7 days in the CLIN-007 study. Specifically, in the CLIN-007 study, CST-2032 (0.3 – 12 mg) was evaluated in healthy volunteers as monotherapy (0.3 – 6 mg, as an oral solution) or with co-administered or pre-administered CST-107 (nadolol, 1 – 40 mg, as oral capsules, or tablets). In addition, the effects on safety, PK and effects on cognition using the using measures from the CANTAB and cerebral perfusion (by ASL MRI) were evaluated in patients with MCI or PD following a single dose of 3 mg CST-2032, administered 2 hours after a single dose of 3 mg CST-107 (nadolol).

The most common AEs with CST-2032 monotherapy (other than skin reactions to ECG electrodes) were increases in heart rate, tremor, palpitations, headache, dizziness and hypokalemia as well as the observed increases in QTc and glucose and decreases in potassium and are consistent with the β_2 -AR agonist drug class. Heart rate generally increased with dose when 1 – 6 mg CST-2032 was administered as monotherapy, with concomitant decreases in plasma potassium concentration. These responses, which are consistent with known effects of β_2 AR agonists, were generally transient with maximal effects at approximately 2 to 3 hours after dosing, at the approximate plasma T_{max} of

CST-2032, and returned to pre-dose levels within 1 day of dosing. These effects were observed at CST-2032 exposures similar to its in vitro β_2 -AR potency, and were minimized by low doses of nadolol at plasma exposures at or above the affinity constant for nadolol at β_2 -AR.

Following CST-2032 monotherapy, increases in QTcF were observed, especially at time points at which decreases in potassium and increases in heart rate were most marked. The time-course of the QTc effects, generally followed the same profile as the changes in potassium and heart rate: with largest changes within the first 4 hours after administration of CST-2032 and returned to pre-dose levels within 1 day of dosing.

Breakthrough increases in QTcF were also observed when sub-optimal doses of nadolol (1 mg) were used in combination with CST-2032. Effects of CST-2032 on potassium, heart rate, and QTcF were attenuated by co-administration and pre-administration of 1 mg of the peripherally restricted β_2 -AR preferring antagonist, nadolol, and essentially eliminated by pre-administration of > 1 mg nadolol. No instances of QTcF > 450 ms or Δ QTcF > 30 ms were observed in subjects who received \geq 3 mg nadolol with CST-2032. The observed potassium concentrations range from 3.8 to 4.3 mmol/L in subjects who received 1, 3, or 10 mg CST-2032 with 3 mg nadolol.

[figure not shown]
The observed increases in QTcF with CST-2032 monotherapy are suspected to be the result of concomitant decreases in potassium that were seen in some individuals. Additionally, it is possible that contribution to these increases arose from inadequate correction for associated heart rate increases using the Fridericia method. The observed increases in QTcF, whether they may be attributed to decreases in potassium or failure to adequately correct for increases in heart rate, are blocked by low doses of nadolol, and thus appear to derive from the primary pharmacological action on β_2 -ARs, consistent with established class effect.

Nonclinical studies with CST-2032 are consistent with a low potential for delayed ventricular polarization. Specifically, from in vitro assessments at cardiac ion channels, a greater than 3000-fold margin was observed between the C_{max} following administration of 3 mg CST-2032 to humans and the potency at the hERG potassium channel. Similarly, a greater than 300-fold margin between was observed between the C_{max} and other cardiac ion channels (Nav1.5, Nav1.5 (late), KCNQ1/mink, Kv4.3/kChIP2, Kir2.1, Cav1.2).

While the data strongly suggest that the apparent QTcF prolongation seen with monotherapy is due to decreases in potassium or failure to adequately correct for increases in heart rate, in an overabundance of caution this study will exclude subjects who have a QTcF > 440 ms or have risk factors for TdP from participating.

Preliminary observations from the CLIN-007 study found that a single dose of 3 mg CST-2032 was associated with improvements in cognition (by CANTAB, [Figure 2](#)) and cerebral perfusion (by ASL MRI, see IB) in healthy volunteers and patients with MCI. Safety and tolerability assessments of CST-2032 administered at a dose of 3 mg with CST-107 has shown a good safety and tolerability profile. Based on all data, a dose of 3 mg of CST-2032 has been selected for this study and will be administered once-daily with a dose of 3 mg CST-107.

Figure 2. Effects of 1, 3, and 10mg CST-2032 Combined with 3 mg CST-107 on CANTAB Measures of Cognition in Healthy Volunteers Aged 50–75 (N=8)

Source: preliminary CANTAB data from CST2032-CLIN-007, Cohort D2. Scales are configured to show improvements as increases from zero. CST-107 dose = 3 mg.

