1.1.2. Rationale for CST-107 Dose Selection

CST-107 (nadolol) is included in this study to attenuate the peripheral effects most commonly caused by CST-2032 and other β_2 -AR agonists. In the phase 1 clinical trial with CST-2032, a range of doses of CST-107 was evaluated to determine the minimum dose at which the observed peripheral β_2 -AR agonist clinical signs (including increased heart rate, palpitations, tremors, decreases in potassium and increases in blood glucose) were attenuated or eliminated. While the latter effects were substantially mitigated following 1 mg CST-107, more robust inhibition of the peripheral effects was observed with 3 mg CST-107. A dose level of 3 mg CST-107 (nadolol) is in marked contrast to the usual initial dose for hypertension which is 40 mg CST-107 tablets once daily. The usual maintenance dose for nadolol is 40 or 80 mg administered once daily and doses up to 240 or 320 mg administered once daily may be needed.

Separate assessments in the CLIN-007 study show that only 2-3% of the plasma concentration of CST-107 is detected in cerebrospinal fluid of healthy volunteers. Furthermore, effects of CST-2032 on measures of cognition using CANTAB and cerebral perfusion were observed in the presence of CST-107.

Taken together, these data support the use of CST-107 as a peripherally restricted β_2 -AR antagonist to mitigate peripheral effects of CST-2032, e.g., on heart rate, while preserving potential central effects on cerebral perfusion, cerebral metabolism, pupillary light reflex, and cognition.

Based on the above experience, after completion of all scheduled assessments and baseline measures on Day -1, an initial dose of 3 mg CST-107 or matching placebo will be administered on Day -1 of each treatment period to provide systemic CST-107 exposure prior to the T_{max} of CST-2032 on Day 1. On subsequent dosing days (Days 1 through 14) in

Treatment periods 1 and 2, 3 mg CST-107 will be co-administered with 3mg CST-2032 as, after the first dose, trough concentrations of CST-107 are predicted to be sufficient to attenuate peripheral effects of CST-2032.

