8.1. Sample Size

A total of approximately 60 subjects is planned. Although formal hypothesis testing is planned, the study is underpowered for detecting meaningful cognitive benefits and lack of significance will not be interpreted as lack of a treatment effect. The sample size is based on practical considerations and is typical of studies whose objectives are to evaluate the safety and cognitive effects of a therapeutic intervention.

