9.2 Secondary Endpoints and Analyses

The FAS will be used for all secondary endpoint analyses unless stated otherwise. All inferential analyses are exploratory in nature given that this study was not powered based on any statistical assumptions.

CANTAB

Cognition function is assessed using the following CANTAB tests:

- Reaction Time (RTI)
- Verbal Recall Memory (VRM)
- Adaptive Tracking Task (ATT)
- Paired Associates Learning Task (PAL)
- Stop Signal Task (SST)
- Delayed Verbal Recall

The cognitive assessments measured as part of the CANTAB tests will be administered on Day - 1 (Baseline), and 3 hours after dosing on Days 1, 7, and 14 of each treatment period. Summaries will be presented by disease type and treatment sequence.

There are eighteen key measures based on the Measures Description downloaded from the CANTAB portal and as described by Cambridge Cognition, which are:

- RTI Median Five-Choice Movement Time: The median time taken for a subject to release the response button and select the target stimulus after it flashed yellow on screen, measured in milliseconds. The measurement name for this parameter in the files downloaded from the CANTAB portal is RTIFMDMT.
- RTI Median Five-Choice Reaction Time: The median duration it took for a subject to release the response button after the presentation of a target stimulus, measured in milliseconds. The measurement name for this parameter in the files downloaded from the CANTAB portal is RTIFMDRT.
- PAL First Attempt Memory Score: The number of times a subject chose the correct box on their first attempt when recalling the pattern locations. The measurement name for this parameter in the files downloaded from the CANTAB portal is PALFAMS.
- PAL Number of Patterns Reached: The number of patterns presented to the subject on the last problem they reached. The measurement name for this parameter in the files downloaded from the CANTAB portal is PALNPR.
- PAL Total Errors (Adjusted): The number of times the subject chose the incorrect box for a stimulus on assessment problems (PALTE), plus an adjustment for the estimated number of

errors they would have made on any problems, attempts and recalls they did not reach. The measurement name for this parameter in the files downloaded from the CANTAB portal is PALTEA.

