11 SAFETY

11.1 Adverse Events

Adverse events (AEs) will be recorded from the time of randomization through end of study. AEs will also be assessed for severity, relationship to study drug, and seriousness. AEs will be considered treatment-emergent if their onset occurs following the date and time of first dose of CST-2032 or matching placebo up to the study completion date. Each TEAE will also be categorized according to the treatment period in which it occurs, in order to attribute and summarize an AE based on treatment received at time of event (i.e., during placebo or active treatment). Events that occur during the washout period between Treatment Period 1 and 2 will be attributed to the treatment received in Period 1, and events occurring after Treatment Period 2 up to the End of Study visit will be attributed to the treatment received in Period 2.

Any missing severity assessments will be assumed to be severe, missing relationship assessments will be assumed to be related, and missing seriousness assessments will be assumed as serious.

An overview of AEs will be produced, including counts and percentages of subjects with any incidences of: treatment-emergent AEs (TEAEs), serious AEs (SAEs), related AEs, unrelated AEs, AEs by maximum severity, AEs leading to treatment withdrawal and AEs leading to death.

Adverse events will be coded based on the Medical Dictionary for Regulatory Affairs (MedDRA 24.1) for reporting by system organ class (SOC) and preferred term (PT) in descending order of overall incidence.

Summaries of adverse events by SOC and PT will include the following types:

- TEAEs;
- SAEs; and
- Related AEs.

A summary of TEAEs by SOC, PT, and maximum severity will also be prepared.

A comprehensive listing of all AEs will be provided in a by-subject data listing. In addition, the following listings will be provided:

- SAEs;
- Related AEs; and
- AEs leading to study drug termination

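### The symptom-type beta-2 effects that the protocol names have no grouped AE count and no within-subject treatment contrast in the SAP

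*Protocol*

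**What the plan says.** Protocol 1.1.1 lists what CST-2032 does without a blocker: the most common AEs, apart from skin reactions to electrodes, "were increases in heart rate, tremor, palpitations, headache, dizziness and hypokalemia". The same section names muscle twitch with tremor among the known class effects. Protocol 1.1.2 then states that "CST-107 (nadolol) is included in this study to attenuate the peripheral effects most commonly caused by CST-2032" and related agonists. For the planned combination, 1.1.1 relies on the earlier CLIN-007 study, in which "there were no instances of tremor, palpitations, dizziness, or tachycardia"; no denominator is given there.

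SAP 11.1 codes AEs "for reporting by system organ class (SOC) and preferred term (PT) in descending order of overall incidence". It plans an overview (any TEAE, SAE, related and unrelated AE, maximum severity, withdrawal, death), SOC/PT tables for TEAEs, SAEs and related AEs, and a table of TEAEs by SOC, PT and maximum severity. Protocol 8.7.1 has the same structure and leaves any additional analyses to the SAP, which adds no grouped count.

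On size, protocol 8.1 says "A total of approximately 60 subjects is planned" and "The sample size is based on practical considerations"; SAP 9.2 adds that "this study was not powered based on any statistical assumptions".

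**The concern.** The safety case concerns a short list of effects that was known in advance. The CLIN-007 statement in support of the combination is itself a grouped one: none of several named symptoms occurred. The Phase 2a outputs do not produce the matching result, namely how many subjects had any of these symptoms on active and how many on placebo.

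With about 60 subjects, each symptom row is likely to hold only a few cases. A modest excess spread over several rows is hard to see, and the overall TEAE row mixes it with unrelated events. The crossover gives each completing subject a placebo period for comparison, yet no AE output uses the pairing. A grouping built after unblinding would also be open to selection of terms.

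**Working it through.** **Step 1: which named effects depend on AE reports alone**

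| Effect | Monotherapy findings, protocol 1.1.1 | CST-107 rationale, protocol 1.1.2 | Measured apart from AEs |
|---|---|---|---|
| Heart rate increase | yes | yes | vital signs, ECG (SAP 11.3, 11.4) |
| Potassium decrease | yes | yes | chemistry, shift tables (SAP 11.2) |
| Glucose increase | yes | yes | chemistry, shift tables (SAP 11.2) |
| QTc increase | yes | no | ECG, QTcF categories (SAP 11.4) |
| Tremor | yes | yes | no |
| Palpitations | yes | yes | no |
| Dizziness | yes | no | no |
| Headache | yes | no | no |

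Dizziness is in the CLIN-007 sentence quoted above; headache is not. The gap concerns the last four rows.

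**Step 2: does any planned output group them or contrast treatments?** None in SAP 11.1 does. SAP 6.1 allows 95% CIs for categorical data where applicable, but that is not a treatment difference. The protocol synopsis plans a within-subject difference in change from baseline for primary endpoints, but defines the difference for continuous endpoints only.

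**Step 3: size, by illustration.** The documents give no AE rates and no power for safety, so there is no figure to reproduce. Everything below rests on assumed rates.

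Inputs: n = 60 subjects, all completing both periods (best case); four symptom terms; risk per term 2% on placebo and 7% on active; periods independent; two-sided exact McNemar test at 5%. Since 2 × 0.5^6 = 0.031 and 2 × 0.5^5 = 0.063, significance needs at least 6 discordant subjects, all in one direction.

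- One row: expected cases 60 × 0.07 = 4.2 against 60 × 0.02 = 1.2. Power 9.9%.
- At least one of four independent rows: 1 − (1 − 0.099)^4 = 34%.
- Four-term group, independent terms: 1 − 0.93^4 = 25.2% against 1 − 0.98^4 = 7.8%, or 15.1 against 4.7 subjects. Power 67%.
- Three-term group without headache: 1 − 0.93^3 = 19.6% against 1 − 0.98^3 = 5.9%. Power 52%.

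Symptoms of one mechanism are probably correlated within a subject. A simulation with a shared normal latent factor (20,000 trials) gives:

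| Latent correlation | At least one of four rows | Four-term group | At least one of three rows | Three-term group |
|---|---|---|---|---|
| 0 | 34% | 67% | 27% | 52% |
| 0.6 | 30% | 42% | 24% | 34% |
| 0.8 | 27% | 32% | 22% | 27% |

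If all terms occur in the same subjects, grouping gains nothing.

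Other assumed rates (1% vs 5%, 2% vs 5%, 3% vs 10%; independent terms): single row 3 to 20%, four-term group 32 to 81%. With 48 pairs at 2% vs 7%: 5% and 54%.

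**Step 4: the same as an interval.** With p10 = pa(1 − pp), p01 = pp(1 − pa) and SE = √{[p10 + p01 − (p10 − p01)²]/60}, where pa and pp are the active and placebo risks:

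- One row: p10 = 0.0686, p01 = 0.0186, SE = 0.0376. Expected difference 5.0 points, half-width 1.96 × 0.0376 = 7.4 points.
- Four-term group, independent terms: p10 = 0.2324, p01 = 0.0581, SE = 0.0658. Expected difference 17.4 points, half-width 12.9 points.

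The single-row interval covers zero; the grouped one does not.

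**The case against.** The strongest reply is that most of the pharmacology is measured. ECG heart rate and QTcF are taken at 1, 2 and 4 hours on Days 1, 7 and 14 of each period, and potassium and glucose at about 4 hours. With assumed SDs for the within-subject difference and 60 pairs, a paired t-test has 89 to 99.7% power for 5 bpm (SD 8 to 12), 86 to 99.9% for 0.2 mmol/L potassium (SD 0.3 to 0.5) and 72 to 97% for 5 ms QTcF (SD 10 to 15). A reader might infer from the AE tables that a residual beta-2 effect would in general be missed. The documents do not support that. The measured data have limits (vital signs and chemistry at about 4 hours against maximal effects at 2 to 3 hours; supine and standing values averaged), but they stand. They do not record symptoms.

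Second, a reader might infer that AEs appear only in single-term rows. The related-AE and severity tables also exist, and SAP 8.6 summarises use of rescue nadolol. This stands as a correction, but none of these isolates the named symptoms, and the related-AE row depends on a causality judgement.

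Third, headache and dizziness are not in the CST-107 rationale, and both add background events. This stands, and it shapes the fix.

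Fourth, setting one preselected row against a group of independent terms flatters grouping. This also stands, so the fair comparator is at least one of several rows, with correlation allowed.

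Fifth, safety is descriptive and no safety test is planned. Power is used here only as a yardstick for how well outputs separate the treatments; low power is not a breach of the plan.

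**Conclusion.** The concern holds in limited form. Tremor or muscle twitch, palpitations, dizziness and headache reach the analysis only as AEs, and neither protocol 8.7.1 nor SAP 11.1 counts subjects with any of them or gives a within-subject contrast. The primary safety analysis is thus less able than it could be to show a residual symptomatic peripheral effect. Heart rate, potassium, glucose and QTcF are outside the point.

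On the assumed 2% vs 7%, grouping four symptoms raises the chance of separating the treatments from about 30 to 34% (any of four rows) to 42 to 67% for latent correlation 0.6 to 0. The gain is smaller for three symptoms or stronger correlation. These figures rest on assumed rates, independence between periods and 60 complete pairs. No statement in the plan is wrong; this is a reporting gap in a descriptive analysis that can be closed cheaply.

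**What to change.** In SAP 11.1, before unblinding:

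1. Fix a preferred term list for tremor/muscle twitch, palpitations/tachycardia and dizziness. Add headache in a second, broader version, because it is non-specific and absent from protocol 1.1.2.
2. For each version, report by treatment the number and percentage of subjects with at least one listed TEAE, with the component rows beneath and the SAP's existing rule for attributing events to periods.
3. Give the within-subject active-minus-placebo risk difference with a 95% CI, in subjects dosed in both periods.
4. Read it beside the heart-rate, potassium, glucose and QTcF summaries, and keep the SOC/PT tables.

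Cost: one paragraph and one table, with no new data. The list must be settled in advance, and the broader version will carry background events.
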